**Labs**

18. At Weeks 36 and 44, the Urine Dipstick will only be performed if clinically indicated (e.g., symptoms of urinary retention or urinary tract infection). Urinalysis will be performed only if the urine dipstick tests positive for the presence of leukocytes, nitrites, or blood cells, and will be performed by the central lab.
19. Urine beta-human chorionic gonadotropin ( $\beta$ -hCG) will be tested for women of childbearing potential only.

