### **7.18.1. Chemistry, Hematology, and Urinalysis (Laboratory Safety Evaluations)**

Laboratory tests for chemistry, hematology, and urinalysis are specified in [Table 4](#). Patients do not need to fast prior to laboratory safety tests.

Analysis of hematology and chemistry will be performed by the central laboratory chosen by the Sponsor. A urine dipstick and urine pregnancy test (for women of childbearing potential) will be performed at the site (supplied by the central laboratory). A sample for urinalysis (including microscopy [RBCs, WBCs, epithelial cells, and bacteria]) AND urine culture will be sent to the central laboratory only if the urine dipstick tests positive for the presence of leukocytes, nitrites, or blood cells. If a patient reports symptoms that are suggestive of a urinary tract infection at any visit, a urine dipstick should be performed and a sample sent for urinalysis and culture, as needed.

If all laboratory values are within the normal reference range, the patient may continue to be evaluated for study entry. If one or more values fall outside the normal range, the Investigator may either exclude the patient from the study or investigate further to determine clinical relevance. Please refer to [Appendix 2](#) for an algorithm for assessing out-of-range laboratory values.

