**Table 4 Laboratory Tests**

Hematology	Chemistry	Urinalysisa	Other
Hematocrit	Albumin	Blood	Serum $\beta$ -human chorionic gonadotropin ( $\beta$ -hCG) b
Hemoglobin	Alkaline phosphatase	Glucose	
Platelet count	Alanine aminotransferase (ALT)	Protein	
WBC (total and differential)	Aspartate aminotransferase (AST)	Specific gravity	
RBC	Bicarbonate	Microscopic exam, (RBCs, WBCs, epithelial cells, and bacteria)	
	Calcium	pH	
	Chloride	Color	
	Creatinine c	Urine pregnancy test ( $\beta$ -hCG)	
	Glucose (fasting or non-fasting)		
	Potassium		
	Sodium		
	Total Bilirubin		
	Direct Bilirubin d		
	Blood Urea Nitrogen		
	Total Cholesterol		

a. A sample for urinalysis and urine culture will be sent to the central laboratory only if the urine dipstick performed at the site tests positive for the presence of leukocytes, nitrites, or blood cells.

b. Urine  $\beta$ -hCG will be tested for women of childbearing potential only. If urine  $\beta$ -hCG is positive, a serum  $\beta$ -hCG must be performed.

c. eGFR will be calculated and reported by the central lab.

d. If total bilirubin is elevated above the upper limit of normal.

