#### **9.4.2. Safety Analysis Populations**

The Safety Analysis (SAF) population will be used for the analysis of safety data in this study. The SAF population consists of all patients who received at least one dose of Study Treatment in this study. Patients will be included in the treatment group corresponding to the Study Treatment they actually received for the analysis of safety data using the SAF population. For most patients, this will be the treatment group to which they were randomized. Patients who take incorrect Study Treatment for the entire Treatment Period will be included in the treatment group corresponding to the Study Treatment actually received. Safety endpoints will be descriptively summarized based on treatment in study RVT-901-3004. This means there will be 2 treatment groups including vibegron (52 weeks and 40 weeks combined) and tolterodine (52 weeks and 40 weeks combined).

At least one laboratory or vital sign measurement obtained subsequent to at least one dose of Study Treatment is required for inclusion in the analysis of each specific parameter. To assess change from baseline, a Baseline measurement is also required.

No imputation will be performed for missing safety data. Baseline will be defined as the last non-missing value before double-blind treatment in study RVT-901-3003. Further inclusion of data from RVT-901-3003 in the reporting of this study will be described in the SAP.

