### **9.5.2. Statistical Methods for Safety Analyses**

Safety analyses will be conducted using the safety population and summarized by treatment group as treated. The treatment-emergent period will be defined as the period of time from the first dose date of the double blinded Study Treatment in this study through 28 days after the last dose of Study Treatment, or the date of initiation of another investigational agent or surgical intervention, whichever occurs first. Safety will be assessed through summaries of adverse events, the frequency of treatment discontinuations due to adverse events, and clinical laboratory evaluations.

The severity of all adverse events will be evaluated by the Investigator as described in Section 8.5. All adverse events will be coded to preferred term and system organ class using MedDRA 20.0 or higher. The incidence of adverse events will be presented by MedDRA system organ class and preferred term, relationship to Study Treatment, and severity.

Laboratory data will consist of chemistry, hematology, and urinalysis data. Only data collected by the central laboratory will be included in the analyses.

Vital signs parameters, including temperature, will be listed and summarized by visit.

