**Appendix-4 Table 1 Monitoring of Liver Tests for Potential Drug-Induced Liver Injury**

Results	Frequency for Repeating Liver (AST, ALT, Bilirubin [Total and Direct]), Alkaline Phosphatase, and INR Tests a
If AST or ALT $\geq 3$ x ULN and total bilirubin $> 2$ x ULN or INR $> 1.5$	Every 24 hours until laboratory abnormalities improve
If ALT or AST $\geq 3$ x ULN and total bilirubin and INR are normal	Every 48 to 72 hours until laboratory abnormalities improve
If the liver test abnormalities improve AND the patient is asymptomatic	Frequency may decrease

Abbreviations: ALT, alanine aminotransferase; AST, aspartate aminotransferase; INR, international normalized ratio; ULN, upper limit of normal

a. Review frequency of monitoring with medical monitor for an individual patient, in case of questions

---

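### The central-laboratory-only rule in Section 9.5.2 leaves urinalysis summaries resting on a reflex-tested subset and leaves the scheduled site dipstick unanalysed

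*Protocol*

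**What the plan says.** Section 9.5.2 defines the laboratory analysis in two sentences. The first sets the content: "Laboratory data will consist of chemistry, hematology, and urinalysis data". The second restricts the source: "Only data collected by the central laboratory will be included in the analyses".

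Section 7.18.1 has the dipstick performed at the site. A sample for urinalysis and culture "will be sent to the central laboratory only if the urine dipstick tests positive for the presence of leukocytes, nitrites, or blood cells". The Labs footnote to the Schedule of Activities repeats the trigger ("Urinalysis will be performed only if the urine dipstick tests positive for the presence of leukocytes, nitrites, or blood cells"), and so does the footnote to Table 4 ("only if the urine dipstick performed at the site tests positive for the presence of leukocytes, nitrites, or blood cells"). Section 7.18.1 adds one further route: a patient reporting symptoms that suggest urinary tract infection has a dipstick, with urine sent as needed.

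The Schedule of Activities marks the dipstick at Weeks 12 (collected under RVT-901-3003), 16, 24 and 52, at Follow-up, and at unscheduled visits. At Weeks 36 and 44 it is done only if clinically indicated.

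Section 9.4.2 governs who is counted, parameter by parameter: "At least one laboratory or vital sign measurement obtained subsequent to at least one dose of Study Treatment is required for inclusion". Change from baseline also needs a baseline value, and missing safety data are not imputed.

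**The concern.** Each rule is ordinary alone. Together they select. The test planned for patients at the main scheduled visits is a site test and falls outside the analysis. The test inside the analysis exists mainly for patients whose site test was already positive. Patients with negative dipsticks and no symptoms have no central result, so they drop out of the urinalysis summaries.

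Safety is the primary objective, and Section 9.5.2 names clinical laboratory evaluations as one of the ways it will be assessed. A reader of the study report would probably take a urinalysis table as describing the treated patients, as the chemistry and hematology tables do. It would instead describe patients who had screened positive or had symptoms. The one urinary laboratory measure obtained regardless of result, dipstick positivity at the scheduled visits, would not be compared descriptively between arms.

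Table 4 also lists glucose, protein, specific gravity, pH and color under urinalysis. These are measured centrally only when a different finding (leukocytes, nitrites or blood cells) triggers the sample, so their summaries are selected as well.

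**Working it through.** The protocol gives no urinalysis rate, dipstick-positivity rate or related figure, so there is nothing to reproduce. The check sets the rules side by side and then writes the consequence as a formula.

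**Step 1. Which data are admitted.** Section 9.5.2 admits central-laboratory data only. The dipstick is performed at the site (7.18.1; Table 4 footnote), so it is out.

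**Step 2. Who has central urinalysis.** Patients with a dipstick positive for leukocytes, nitrites or blood cells (7.18.1; Labs footnote; Table 4 footnote), plus some patients with urinary symptoms (7.18.1). Both routes are selected.

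**Step 3. Who is counted.** Patients with at least one post-dose value of the parameter, with a baseline value as well for change from baseline, and no imputation (9.4.2). No section brings dipstick-negative patients into the urinalysis summary. Chemistry and hematology are drawn at scheduled visits whatever the result, so they are not affected.

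**Step 4. Effect on a percentage.** Let N be the patients dipsticked in an arm, d the share positive, and q the share of those abnormal on central testing. Ignore the symptom route, and take dipstick-negative patients as not abnormal. That is tenable only for findings tied to leukocytes, nitrites and blood.

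- Patients tested centrally: N × d
- Patients abnormal: N × d × q
- Percentage among measured patients: (N × d × q) / (N × d) = q
- Percentage among all dipsticked patients: (N × d × q) / N = d × q
- Ratio of the two: 1/d, which exceeds 1 for any d below 100%

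Illustration only. The values of d and q are assumptions, and N is the planned arm size in the Synopsis (267 + 233 = 500), as if every patient were dipsticked.

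- For d from 10% to 40%, the number tested is 267 × 0.10 = 27 to 267 × 0.40 = 107 on vibegron, and 233 × 0.10 = 23 to 233 × 0.40 = 93 on tolterodine.
- The ratio 1/d runs from 10 down to 2.5.
- For q from 30% to 70%, the percentage over all patients runs from 0.10 × 0.30 = 3% to 0.40 × 0.70 = 28%, where the percentage among measured patients is 30% to 70%.

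**Step 5. Effect on a comparison of arms.** Suppose d is 20% in one arm and 40% in the other, with q = 50% in both (all assumed). Among measured patients the arms show 50% and 50%. Over all dipsticked patients they show 0.20 × 0.50 = 10% and 0.40 × 0.50 = 20%. The percentages agree exactly only because q is assumed equal.

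**Step 6. Effect on change from baseline.** A patient needs central urinalysis at both times. Assume RVT-901-3003 used the same trigger and that d = 20% at each time. The number of vibegron patients with both values is then 267 × 0.20 × 0.20 = 11 if the two results are independent, and 267 × 0.20 = 53 if they always agree.

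**The case against.** **The SAP may settle it.** Section 9 calls itself a brief summary and leaves full details to the SAP. The protocol names no urinalysis abnormality percentage, and Section 9.4.2 can be read as an evaluability rule rather than a denominator. This stands in part: the q versus d × q contrast applies only if percentages among measured patients are shown. But means and changes from baseline would be computed on the same subset. The source restriction is also a stated rule. A SAP can label the tables, but it cannot admit dipstick results without departing from Section 9.5.2.

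**The dipsticks are supplied by the central laboratory.** They are, but the test is performed at the site, so on the ordinary reading the results are not collected by the central laboratory.

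**Urinary infection is captured elsewhere.** This stands, and it limits the point. Section 8.6 makes events suggestive of cystitis or urinary tract infection adverse events of clinical interest. Treatment-emergent adverse events are summarised in all treated patients. A reader might infer that a difference between arms in urinary infection would go unseen. The documents do not support that: clinical infection is counted on the full safety population. Nor would a difference in dipstick positivity necessarily be hidden altogether, since it would show indirectly if the number tested per arm were printed. The narrower statement is that positivity itself is not analysed.

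**Negative dipsticks could simply be counted as normal urinalysis.** They should not be. A dipstick negative for leukocytes, nitrites and blood says nothing about protein, glucose, pH or specific gravity, and the step would also conflict with the no-imputation rule.

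**Conclusion.** The point holds in a limited form. Under the protocol's own rules, urinalysis summaries and changes from baseline describe patients selected by a positive dipstick or by symptoms, and arm differences in dipstick positivity are not analysed. This follows from the text alone.

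Its size cannot be computed from the protocol. A percentage among measured patients exceeds the percentage over all dipsticked patients by 1/d, and d is not given. The formula assumes that dipstick-negative patients have no abnormality of the trigger findings, and it leaves out the symptom route.

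The consequence is modest: safety is descriptive, there are no formal comparisons, and clinical urinary events have their own full-population reporting. What is affected is laboratory findings that do not become adverse events.

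A reader might extend the point to repeat liver tests in Appendix 4 and infer that the restriction discards them. The documents do not support this. Section 7.18.1 assigns chemistry to the central laboratory, and no section says the repeats are done locally. Liver abnormalities that require withholding treatment are reported separately under Sections 8.6 and 8.6.1.

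**What to change.** In Section 9.5.2:

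- Exempt the site dipstick from the central-laboratory restriction.
- Report dipstick positivity for leukocytes, nitrites and blood by arm and visit, with all patients dipsticked at Weeks 16, 24, 52 and Follow-up as denominator.
- Show Weeks 36 and 44 and unscheduled dipsticks separately, because they are done only if clinically indicated.
- Label central urinalysis summaries, including protein, glucose, pH and specific gravity, as conditional on reflex testing. Give the numbers dipsticked, positive and sent per arm and visit.
- Do not set untested analytes to normal.

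The cost is a wording change, one derived variable and one added table, with no new procedure for patients. Two cautions apply. The protocol does not say that dipstick results are entered in the eCRF, so this must be confirmed. Site-read results are also less standardised than central ones. If dipstick results are not recorded, the labelling and the number of samples tested centrally remain the minimum.

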### **9.6. Multiplicity**

All efficacy endpoints will be considered descriptive and no multiplicity adjustments will be performed for these endpoints.

### **9.7. Sample Size Determination**

Five hundred (500) patients rolling over from study RVT-901-3003, in addition to other long-term safety data with vibegron, is sufficient to characterize the long-term safety profile of vibegron 75 mg once daily and satisfies the ICH guidance for 1-year exposure.

### **9.8. Interim Analyses**

There is no planned interim analysis for efficacy.

## **10. STUDY GOVERNANCE CONSIDERATIONS**

### **10.1. Financial Disclosure**

Financial disclosure requirements are outlined by the US Code of Federal Regulations Title 21, Part 54 (21 CFR 54), Financial Disclosure by Clinical Investigators. It is the Sponsor's responsibility to determine, based on these regulations, whether a request for financial disclosure information is required. It is the Investigator's and Sub-Investigator's responsibility to comply with any such request.

This is a “covered clinical study”, defined under 21 CFR 54 as “any study of a drug or device in humans submitted in a marketing application or reclassification petition patient to this part that the applicant or FDA relies on to establish that the product is effective (including studies that show equivalence to an effective product) or any study in which a single Investigator makes a significant contribution to the demonstration of safety.” As such, all Investigators and Sub-Investigators must provide documentation of their financial interest or arrangements with the Sponsor, or proprietary interests in the drug being studied. This documentation must be provided before participation of the Investigator and any Sub-Investigator. The Investigator and Sub-Investigator agree to notify the Sponsor of any change in reportable interests during the study and for 1 year following completion of the study.

### **10.2. Data Management**

Patient data will be entered into a Sponsor-approved electronic database and combined with data provided from other sources in validated datasets then transmitted electronically to the Sponsor or designee.

Management of clinical data will be performed in accordance with applicable Sponsor-approved standards and data cleaning procedures to ensure the integrity of the data (e.g., errors will be corrected and inconsistencies clarified).

Adverse events and concomitant medications terms will be coded using the most current versions of the MedDRA (i.e., 20.0 or higher) and the World Health Organization Drug Dictionary Enhanced (WHO-DDE), respectively.

The Investigator will retain original source documents and the Sponsor will receive eCRF-required data as electronic datasets. Patient initials will not be collected or transmitted to the Sponsor.

### **10.3. Monitoring**

This study will be monitored by the Sponsor (or designee) in accordance with current GCP regulations. By signing this protocol, the Investigator grants permission to the Sponsor (or designee) and appropriate regulatory authorities to conduct on-site monitoring of all appropriate study documentation. In order to verify the accuracy of data collected in the eCRF, the monitor will require direct access to original source documents (e.g., patient records, patient charts, and laboratory reports).

During the review of these documents, the anonymity of the patient will be respected with strict adherence to professional standards of confidentiality. A study monitor will contact and visit the

site regularly and will be allowed, on request at a mutually acceptable time, to inspect the various records of the study. It will be the study monitor's responsibility to inspect the eCRF at regular intervals throughout the study, to verify the adherence to the protocol and the completeness, correctness, and accuracy of all eCRF entries, and to meet with the Investigator to discuss study progress and compliance with the protocol and GCP. The study monitor should have access to laboratory test results and any other source records and data needed to verify the entries on the eCRF. The Investigator agrees to cooperate with the study monitor to ensure that any problems detected in the course of these monitoring visits are resolved.

#### **10.4. Auditing or Inspections**

Representatives of regulatory authorities, health authorities, the Sponsor, or IRB/REB/IEC's may conduct inspections or audits of the clinical study. If the Investigator is notified of an inspection by a regulatory authority, the Investigator agrees to notify the Sponsor's medical monitor immediately. By signing this protocol, the Investigator agrees to provide to appropriately qualified personnel from such groups, access to records, facilities, and personnel for the effective conduct of any inspection or audit.

#### **10.5. Study Oversight Committees**

##### **10.5.1. Clinical Adjudication Committee**

As noted in Section 8.6, MACCE event diagnosis will be adjudicated by an independent external expert committee.

##### **10.5.2. Steering Committee**

A Steering Committee may be formed, if deemed necessary. If formed, the committee will be comprised of both Sponsor and non-Sponsor scientific experts who will participate in the design, conduct, analyses, and publication of the study. Steering Committee members will remain blinded to patients' treatment assignments and all unblinded data until the database is officially locked and unblinded.

#### **10.6. Protocol Modifications**

Protocol modifications, except those intended to reduce immediate risk to patients, may be made only by the Sponsor. All protocol modifications must be submitted to the IRB/REB/IEC in accordance with local requirements. Approval must be obtained before changes can be implemented. The Investigator must not deviate from the protocol without first obtaining approval from the Sponsor and the IRB/REB/IEC, if required. In medical emergencies, the Investigator will use medical judgment and will remove the patient from immediate hazard, then notify the Sponsor (or designee) and the IRB/REB/IEC immediately regarding the type of emergency and the course of action taken. The Investigator must notify the Sponsor (or designee) of any inadvertent protocol deviations upon their discovery, and document the deviations appropriately in the study files.

When a protocol amendment substantially alters the study design or the potential risks or burden to patients, the informed consent form will be amended and approved by the IRB/REB/IEC, and all patients on treatment will again provide informed consent.

## **10.7. Study Discontinuation**

The Sponsor reserves the right to terminate the study at any time. Should this be necessary, the Sponsor will arrange discontinuation procedures and notify the appropriate regulatory authority(ies) and IRB/REB/IEC. In terminating the study, the Sponsor and the Investigator will assure that adequate consideration is given to the protection of the study participants' interests.

## **10.8. Publications**

After conclusion of the study and without prior written approval from the Sponsor, Investigators in this study may communicate, orally present, or publish in scientific journals or other scholarly media only after the following conditions have been met:

- The results of the study in their entirety have been publicly disclosed by or with the consent of the Sponsor in an abstract, manuscript, or presentation form; or
- The study has been completed at all study sites for at least 5 years.

No such communication, presentation, or publication will include Urovant Sciences GmbH confidential information (see Section 10.9.5).

The Investigator will submit to the Sponsor any proposed publication or presentation along with the respective target scientific journal or presentation forum at least 30 days before submission of the publication or presentation. The Investigator will comply with Sponsor requests to delete references to its confidential information (other than the study results) in any paper or presentation and agrees to withhold publication or presentation for an additional 60 days in order to obtain patent protection if deemed necessary.

